6.3. Lifestyle and/or Dietary Requirements

Throughout the study, subjects may undergo medical assessments and review of compliance with requirements before continuing in the study.

6.3.1. Meals and Dietary Restrictions

Standardized meals will be provided during each subject's stay in the CRU (except when test meals are administered prior to dosing).

Administration of LY3337641 in the fasted state

Following an overnight fast of at least 10 hours, subjects will be administered 20 mg LY3337641 with approximately 240 mL water. Water can be allowed as desired except from 1 hour before until 1 hour after drug administration. No food will be allowed for at least 4 hours postdose,

after which time a standardized meal will be provided. Meals will be provided as appropriate at all other times.

Administration of LY3337641 in the fed state

Following an overnight fast of at least 10 hours, subjects will start a Food and Drug Administration (FDA)-defined high-fat meal 30 minutes prior to administration of LY3337641. It is intended that the meals will be ingested in their entirety over an approximate 25-minute period, such that they are completed at least 5 minutes before dosing. A 20-mg dose of LY3337641 will be given with approximately 240 mL of water. Water can be given as desired, except for 1 hour before and 1 hour after drug administration. No further food will be permitted until at least 4 hours postdose, after which time a standardized meal will be provided. Meals will be provided as appropriate at all other times.

High-fat meal

The high-fat meal (fat comprises approximately 50% of total calorific content) should consist of approximately 800 to 1000 calories in total. No additional food or substitute is allowed. An example of a typical test meal is 2 eggs fried in butter, 2 strips of bacon, 2 slices of toast with butter, 4 ounces of hash brown potatoes, and 8 ounces of whole milk. The test meal derives approximately 150, 250, and 500 to 600 calories from protein, carbohydrate, and fat, respectively.

6.3.2. Caffeine, Alcohol, and Tobacco

Caffeine – Subjects will refrain from consuming xanthine- or caffeine-containing food and drinks from 48 hours prior to admission in each study period, and while resident in the CRU. Examples of these food and drinks include coffee, tea, cola drinks and chocolate.

Alcohol – Subjects will not consume alcohol for 48 hours prior to admission in each study period, and while resident in the CRU.

Smoking – Subjects should not smoke or use any nicotine products from 2 hours prior to each admission until after collection of the 72-hour PK sample.

6.3.3. Activity

No strenuous activity will be allowed for 48 hours prior to admission and during the study.

6.3.4. Contraception

Male subjects

Male subjects or their partners will be required to use an effective method of contraception during the study and for 90 days after the last dose of study drug. Acceptable methods of contraception may include:

- Condom (male condom or female condom) in conjunction with spermicidal gel, foam, cream, film, or suppository.

- Diaphragm or cervical vault cap used in conjunction with spermicidal gel, foam, cream, film, or suppository.
- Male sterilization, with the appropriate post-vasectomy documentation of the absence of sperm in the ejaculate.
- True abstinence (this must be due to subject's lifestyle choice; ie, the subject should not become abstinent just for the purpose of study participation). Withdrawal or calendar methods are not considered acceptable.
- Female partner with placement of an effective hormonal intrauterine device.
- Female partner with established use of oral, injected, or implanted hormonal methods of contraception.

Sexual intercourse with pregnant partners should also be avoided during the course of the study unless condoms are used from the time of the first dose until 28 days after dosing.

Male subjects must agree not to donate sperm for the duration of the study and for 90 days following the last dose of study drug

Female subjects of child-bearing potential

Female subjects of child-bearing potential must agree to use one highly effective method of contraception or a combination of 2 effective methods of contraception during the study and for 28 days following the last dose of study drug.

Highly effective methods of contraception are contraceptive measures with a failure rate of <1% per year, and include:

- Intrauterine device (IUD; eg, Mirena). Steel or copper IUDs are not acceptable.
- Established use of oral, implanted, transdermal, or hormonal method of contraception associated with inhibition of ovulation.
- Male sterilization, with verbal confirmation of surgical success
- Bilateral tubal ligation.

6.4. Screen Failures

Individuals who do not meet the criteria for participation in this study (screen failure) may not be re-screened.

7. Treatment

7.1. Treatment Administered

This study involves comparisons of different formulations of LY3337641. LY3337641 will be administered at a dose of 20 mg in each treatment period.

The treatment arms are as follows:

- Reference formulation (R_{fasted}): 20 mg LY3337641 Phase 1/2 tablet (diHCl salt) administered in the fasted state;
- Test formulation 1 ($T1_{\text{fasted}}$): 20 mg LY3337641 commercial image tablet (esylate salt) administered in the fasted state;
- Test formulation 1 ($T1_{\text{fed}}$): 20 mg LY3337641 commercial image tablet (esylate salt) administered in the fed state;
- Test formulation 2 ($T2_{\text{fasted}}$): 20 mg LY3337641 large API PSD commercial image tablet (esylate salt) administered in the fasted state.

The investigator or designee is responsible for:

- explaining the correct use of the investigational products to the site personnel;
- verifying that instructions are followed properly;
- maintaining accurate records of investigational product dispensing and collection;
- returning all unused medication to Lilly or its designee at the end of the study.

Note: In some cases, sites may destroy the material if, during the investigative site selection, the evaluator has verified and documented that the site has appropriate facilities and written procedures to dispose of clinical trial materials.

7.1.1. Packaging and Labeling

Tablets containing 20 mg LY3337641 will be provided to the site.

Multiple subjects may be dosed from a single package.

Clinical trial materials will be labeled according to the country's regulatory requirements. Packages will be labeled to distinguish each tablet in the dosing schedule:

- Phase 1/2 diHCl salt (reference formulation)
- Commercial image tablet (esylate salt) (test formulation 1)
- Large API PSD commercial image tablet (esylate salt) (test formulation 2)

There is no requirement to store retention samples.

7.2. Method of Treatment Assignment

Subjects will be randomized to 1 of 4 treatment sequences using a computer-generated allocation schedule.

7.2.1. Selection and Timing of Doses

The doses will be administered at approximately the same time on each dosing day. The actual time of all dose administrations will be recorded in the subject's case report form (CRF).

7.3. Blinding

This is an open-label study.

7.4. Dose Modification

Dose reductions or adjustments will not be allowed during this study.

7.5. Preparation/Handling/Storage/Accountability

Only participants enrolled in the study may receive investigational product and only authorized site staff may supply or administer study treatment. All study treatments should be stored in an environmentally controlled and monitored (manual or automated) area in accordance with the labeled storage conditions with access limited to the investigator and authorized site staff.

The investigator or designee is responsible for study treatment accountability, reconciliation, and record maintenance (such as receipt, reconciliation and final disposition records).

7.6. Treatment Compliance

The investigational product will be administered at the clinical site, and documentation of treatment administration will occur at the site.

7.7. Concomitant Therapy

The use of topical medication, provided there is no evidence of chronic dosing with the risk of systemic exposure, and occasional acetaminophen/ibuprofen is acceptable at the discretion of the investigator. Additional drugs are prohibited during the study unless required to treat an AE.

If the need for concomitant medication arises, inclusion or continuation of the subject may be at the discretion of the investigator with consultation with a Lilly clinical pharmacologist or clinical research physician. Any additional medication used during the course of the study must be documented.

7.8. Treatment after the End of the Study

This section is not applicable to this study.

8. Discontinuation Criteria

8.1. Discontinuation from Study Treatment

Subjects who discontinue the investigational product early will have procedures performed as shown in the Schedule of Activities (Section 2).

8.1.1. Discontinuation of Inadvertently Enrolled Subjects

If the Sponsor or investigator identifies a subject who did not meet enrollment criteria and was inadvertently enrolled, a discussion must occur between the Lilly CP/CRP and the investigator to determine if the subject may continue in the study. If both agree it is medically appropriate to continue, the investigator must obtain documented approval from the Lilly CP/CRP to allow the inadvertently enrolled subject to continue in the study with or without continued treatment with investigational product.

8.2. Discontinuation from the Study

Subjects will be discontinued in the following circumstances:

- enrollment in any other clinical trial involving an investigational product or enrollment in any other type of medical research judged not to be scientifically or medically compatible with this study;
- participation in the study needs to be stopped for medical, safety, regulatory, or other reasons consistent with applicable laws, regulations, and good clinical practice (GCP);
- Investigator Decision:
 - the investigator decides that the subject should be discontinued from the study;
 - if the subject, for any reason, requires treatment with another therapeutic agent that has been demonstrated to be effective for treatment of the study indication, discontinuation from the study occurs prior to introduction of the new agent;
- Subject Decision:
 - the subject, or designee, for example, parents or legal guardian requests to be withdrawn from the study.

8.3. Subjects Lost to Follow-up

A subject will be considered lost to follow-up if he or she repeatedly fails to return for scheduled visits and is unable to be contacted by the study site. Site personnel are expected to make diligent attempts to contact subjects who fail to return for a scheduled visit or were otherwise unable to be followed up by the site.

9. Study Assessments and Procedures

Section 2 lists the Schedule of Activities, detailing the study procedures and their timing.

Appendix 2 lists the laboratory tests that will be performed for this study.

Appendix 4 provides a summary of the maximum number and volume of invasive samples, for all sampling, during the study.

Unless otherwise stated in subsections below, all samples collected for specified laboratory tests will be destroyed within 60 days of receipt of confirmed test results. Certain samples may be retained for a longer period, if necessary, to comply with applicable laws, regulations, or laboratory certification standards.

Investigators must document their review of each laboratory safety report.

9.1. Efficacy Assessments

This section is not applicable for this study.

9.2. Adverse Events

Investigators are responsible for monitoring the safety of subjects who have entered this study and for alerting Lilly or its designee to any event that seems unusual, even if this event may be considered an unanticipated benefit to the subject.

The investigator is responsible for the appropriate medical care of subjects during the study.

The investigator remains responsible for following, through an appropriate health care option, AEs that are serious or otherwise medically important, considered related to the investigational product or the study, or that caused the subject to discontinue the investigational product before completing the study. The subject should be followed until the event resolves, stabilizes with appropriate diagnostic evaluation, or is reasonably explained. The frequency of follow-up evaluations of the AE is left to the discretion of the investigator.

After the informed consent form (ICF) is signed, study site personnel will record, via eCRF, the occurrence and nature of each subject's preexisting conditions, including clinically significant signs and symptoms of the disease under treatment in the study. Additionally, site personnel will record any change in the condition(s) and the occurrence and nature of any AEs.

The investigator will interpret and document whether or not an AE has a reasonable possibility of being related to study treatment or a study procedure, taking into account the disease, concomitant treatment or pathologies.

A "reasonable possibility" means that there is a cause and effect relationship between the investigational product, study device and/or study procedure and the AE.

Planned surgeries should not be reported as AEs unless the underlying medical condition has worsened during the course of the study.

If a subject's investigational product is discontinued as a result of an AE, study site personnel must report this to Lilly or its designee via eCRF.

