9.2.1. Serious Adverse Events

An SAE is any AE from this study that results in one of the following:

- death;
- initial or prolonged inpatient hospitalization;
- a life-threatening experience (that is, immediate risk of dying);
- persistent or significant disability/incapacity;
- congenital anomaly/birth defect;
- events considered significant by the investigator based upon appropriate medical judgment.

Study site personnel must alert Lilly, or its designee, of any SAE within 24 hours of investigator awareness of the event via a sponsor-approved method. If alerts are issued via telephone, they are to be immediately followed with official notification on study-specific SAE forms. This 24-hour notification requirement refers to the initial SAE information and all follow-up SAE information.

Although all AEs are recorded in the eCRF after signing informed consent, SAE reporting begins after the subject has signed informed consent and has received investigational product. However, if an SAE occurs after signing informed consent, but prior to receiving Investigational product (IP), AND is considered reasonably possibly related to a study procedure then it MUST be reported.

Investigators are not obligated to actively seek AEs or SAEs in subjects once they have discontinued from and/or completed the study (the subject summary CRF has been completed). However, if the investigator learns of any SAE, including a death, at any time after a subject has been discharged from the study, and he/she considers the event reasonably possibly related to the study treatment or study participation, the investigator must promptly notify Lilly.

Pregnancy (maternal or paternal exposure to IP) does not meet the definition of an adverse event. However, to fulfill regulatory requirements any pregnancy should be reported following the SAE process to collect data on the outcome for both mother and fetus.

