9.2.1.1. Suspected Unexpected Serious Adverse Reactions

Suspected unexpected serious adverse reactions (SUSARs) are serious events that are not listed in the IB and that the investigator identifies as related to IP or procedure. United States 21 CFR 312.32 and European Union Clinical Trial Directive 2001/20/EC and the associated detailed guidances or national regulatory requirements in participating countries require the reporting of SUSARs. Lilly has procedures that will be followed for the recording and expedited reporting of SUSARs that are consistent with global regulations and the associated detailed guidances.

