10.3.1. Safety Analyses

10.3.1.1. Clinical Evaluation of Safety

All drug-related and procedural AEs will be listed, and if the frequency of events allows, safety data will be summarized using descriptive methodology.

The incidence of symptoms for each treatment will be presented by severity and by association with IP as perceived by the investigator. Symptoms reported to occur prior to enrollment will be distinguished from those reported as new or increased in severity during the study. Each symptom will be classified by the most suitable term from the medical regulatory dictionary.

The number of drug-related SAEs will be reported.

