9.4 Safety and Tolerability Assessments

9.4.1 Adverse events

Where changes in severity are recorded in the Case Report Form (CRF), each separate severity of the AE will be reported in the listings, only the most severe will be used in the summary tables. A pre-existing condition is defined as an AE that starts before the subject has provided written informed consent and is ongoing at consent. A non-treatment emergent AE is defined as an AE which starts after informed consent but prior to dosing. A treatment-emergent AE is defined as an AE which occurs postdose or which is present prior to dosing and becomes more severe postdose.

All AEs will be listed. Treatment-emergent AEs will be summarized by treatment, severity and relationship to the study drug. The frequency (the number of AEs, the number of subjects experiencing an AE and the percentage of subjects experiencing an AE) of treatment-emergent AEs will be summarized by treatment, Medical Dictionary for Regulatory Activities (MedDRA) version 19.1 system organ class and preferred term. The summary and frequency AE tables will be presented for all causalities and those considered related to the study drug. Any serious AEs will be tabulated.

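### Protocol 9.2 asks whether an AE is possibly related, then defines that possibility as an actual causal relationship; the two thresholds need to be reconciled.

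*Protocol*

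**What the plan says.** Protocol 9.2 gives the causality question and its key term in adjacent sentences. The investigator must document whether an AE "has a reasonable possibility of being related to study treatment or a study procedure", taking other possible explanations into account. The protocol then says that a *reasonable possibility* "means that there is a cause and effect relationship between the investigational product" (or a device or procedure) and the AE.

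Relatedness is used again in these places:

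- Protocol 9.2.1, for an SAE after consent but before the first dose: if the event "is considered reasonably possibly related to a study procedure then it MUST be reported".
- Protocol 9.2.1, for an SAE that the investigator learns of after discharge: the sponsor must be told if "he/she considers the event reasonably possibly related to the study treatment or study participation".
- Protocol 9.2.1.1: a SUSAR is a serious event absent from the Investigator's Brochure and "that the investigator identifies as related to IP or procedure".
- Protocol 10.3.1.1: drug-related and procedural AEs are listed, symptoms are presented by perceived association with the product, and "The number of drug-related SAEs will be reported".
- SAP 9.4.1: the AE summary and frequency tables are given "for all causalities and those considered related to the study drug".

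**The concern.** A possibility of a causal link is a lower bar than the existence of one. The definition has no qualifier such as *may* or *suspected*, so it replaces the threshold of the question with a stricter one. An investigator who follows the definition to the letter would record a possibly related event as not related.

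The error can run in one direction only, towards fewer events called related, and for a safety classification that is the less cautious direction. At stake are the relatedness flag itself, the outputs built on it, and those few reporting duties that apply only when the investigator judges an event related.

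**Working it through.** No arithmetic applies: the plan states no figure on this point. The check is a comparison of the two sentences, followed by a trace of each use of relatedness.

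**Step 1: where the two sentences differ.** Sort AEs by the investigator's view:

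- (a) Causation is accepted. Related under both sentences.
- (b) Causation is reasonably possible but not established. Related under the question, not related under the literal definition.
- (c) No reasonable possibility. Not related under both.

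Only group (b) changes, and only from related to not related.

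**Step 2: whether anything corrects the definition.** Protocol Appendix 1 does not define the term. SAP 9.4.1 refers to relationship to study drug without defining it. No other section restates or replaces the sentence in Protocol 9.2.

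**Step 3: what depends on the flag.**

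- Related-AE tables (SAP 9.4.1) and the related listing, symptom presentation and drug-related SAE count (Protocol 10.3.1.1): these use the flag directly.
- SUSAR classification (Protocol 9.2.1.1): depends on the flag as far as it rests on the investigator's identification of the event as related.
- SAEs between consent and first dose, and SAEs learned of after discharge (Protocol 9.2.1): both rules use *reasonably possibly related*, close to the term that 9.2 defines. For these events the causality judgement decides whether the stated duty to report applies.

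**Step 4: what does not depend on it.**

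- Post-dose SAEs on study: any SAE is notified within 24 hours, with no causality condition (Protocol 9.2.1).
- AE recording: all AEs after consent go into the eCRF, including those before dosing (Protocol 9.2.1).
- AE follow-up: relatedness is one of several alternative triggers. Serious or medically important AEs, and those that lead to discontinuation of the product, are followed in any case (Protocol 9.2).
- SAP 9.4.1 outputs: all AEs are listed, any serious AEs are tabulated, and all-causality tables stand beside the related ones.
- TEAE incidence, the tolerability endpoint: the TEAE definition in Protocol Appendix 1 needs no causal relationship.
- PK endpoints: relatedness plays no part.

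**The case against.** The strongest reply is that the literal reading is not the only one. The operative instruction still asks about a possibility, and the defining sentence can be taken to say what the possibility is *of*: a causal link, as opposed to mere timing. Protocol 9.2.1 twice speaks of events that are possibly related, and Protocol 10.3.1.1 reports association as the investigator perceives it. An experienced investigator may well apply the ordinary meaning. This stands as a reason to call under-calling a risk. It does not remove the contradiction, because the sentence is framed as a definition and nothing says that the ordinary meaning prevails.

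The second reply is that safeguards limit the consequences. This largely stands. Besides those in step 4, the investigator must alert the sponsor to any event that seems unusual (Protocol 9.2), and the sponsor reviews SAEs and AE trends (Protocol 9.4.4). Protocol 9.2.1.1 does not use the defined term, and it commits the sponsor to SUSAR procedures consistent with global regulations. The SAP also supersedes the protocol's statistical considerations (SAP 3), so the narrower AE listing in Protocol 10.3.1.1 gives way to a listing of all AEs. These safeguards do not correct the relatedness flag itself, and they do not create a causality-free reporting duty for SAEs before dosing or after discharge.

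A reader might go further and infer that serious events on study would go unreported, or that each under-called event is a missed expedited report. The documents do not support this: the sponsor is told of every post-dose SAE on study whatever its causality, and has its own SUSAR procedures.

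**Conclusion.** The point holds as a contradiction between two adjacent sentences of Protocol 9.2, with limited consequences. If the definition is followed as written, possibly related events are misclassified as not related. The exposure is confined to the relatedness flag and the outputs built on it, SUSAR classification where it rests on that flag, and mandatory reporting of procedure-related SAEs before dosing and of SAEs learned of after discharge. The conclusion assumes that some investigators would apply the definition literally, and that the two reporting rules in Protocol 9.2.1 take their meaning from 9.2; the documents settle neither.

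The size cannot be estimated. A reader might try to scale up from the 20-mg arm of Study JPDD, where 4 of 6 subjects reported 6 TEAEs and one was attributed to drug (Protocol 3.3). That would tell us nothing about under-calling: the documents give no misclassification rate and do not say which causality definition that study used. If it was the same one, the single attributed event already includes any under-calling.

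**What to change.** Reword the defining sentence in Protocol 9.2 so that it keeps the threshold of the sentence before it: the term means a reasonable possibility that the product, device or procedure caused the AE, without causation having to be established. Use that term in Protocol 9.2.1, 9.2.1.1 and 10.3.1.1, and state in SAP 9.4.1 that the related-AE tables use it.

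The cost is one reworded sentence, matching terms in the sections named, and a brief note in investigator training. Somewhat more AEs may be labelled related. Nothing in the design, sample size or PK analysis changes.
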